1. JUSTIFICATION FOR THE STUDY

1.1. POSITIONING OF THE RESEARCH

With the increase in life expectancy among the French population, there has been a rise in the number of patients with fractures of the upper femur (FESF), particularly among the elderly. In France, the number of hospital stays for UEF has been increasing by 0.3% per year since 1998, and the incidence remains predominantly female. The crude incidence rate of UEF was 42.1/10,000 for people over 55 years of age in 2007. UEF mainly affects elderly and very elderly people. There has been a gradual increase in the average age of fracture patients. Again in 2007, patients over 80 years of age accounted for 60% of male patients operated on for FESF and 70% of female patients (1). This is a serious condition, with the risk of death increasing with age. It is 2% in women under 80 during hospitalisation, rising to 8.3% in those over 95. This mortality rate is higher in men, reaching 15% in men over 94 during hospitalisation (1). Longer-term mortality rates vary according to studies, from 14.7% at one year (2) to 46% at one year in patients over 90 years of age (3). However, there has been a gradual decrease in this mortality rate in France, probably due to improved surgical and perioperative care for patients (4).

Anaemia is common in the geriatric population. In a survey of a hospitalised geriatric population, 24% of patients had anaemia, the aetiology of which was iron deficiency in 15% of cases (5). It is also common in surgery, particularly in the perioperative period. In a study of 546 patients with fractures of the upper femur, 40.4% had anaemia on admission and 93.0% had anaemia postoperatively (6).

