- **Foss's work (2008)** found a link between haemoglobin levels in the first three days post-operatively (487 patients, all ages combined) and patient mobility during those first three days ($p < 0.05$, before any transfusion). Independent risk factors for inability to walk were age over 75, dementia, reduced pre-fracture mobility, the presence of post-operative complications, and haemoglobin below 10 g/dL. Patients were treated according to a specialised perioperative rehabilitation protocol [*surgery within 24 hours, spinal anaesthesia, epidural analgesia for 96 hours postoperatively, oral high-protein supplementation, daily 30-minute physiotherapy sessions from the first day*] (18).
- **Halm (2004)** conducted a prospective observational study of 550 patients over the age of 50. High pre- or post-operative haemoglobin levels were correlated with a reduction in length of hospital stay and readmission rates, but not with motor function scores (ability to walk and climb stairs, at day 60, assessed by telephone interview) [*adjusted for age, sex, pre-fracture functional status, dementia, institutionalisation, transfusion*] (19).
- **Gruson (2002)** showed that anaemia on admission in 395 patients over the age of 65 (from 1991 to 1997) with a femoral neck fracture was correlated with a longer hospital stay and higher mortality at 6 and 12 months. A telephone call at 3, 6 and 12 months allowed for the assessment of an ADL and Instrumental Activities of Daily Living (IADL) score and functional autonomy, which were no different between anaemic and non-anaemic patients [*patients who were previously autonomous, living at home and without cognitive impairment; based solely on anaemia on admission*] (20).

- **Maraldi (2006)** analysed 56,752 patients over the age of 65 hospitalised in geriatrics (medicine sector). The recovery of independence at the end of hospitalisation was less significant in anaemic patients than in non-anaemic patients ($p < 0.001$).

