2.1.2. Primary evaluation criterion

- Haemoglobin level on day 5 post-operatively (considered the post-operative haemoglobin reference level in this study)
 - In the case of patients who received a transfusion postoperatively, the reference haemoglobin level will be the haemoglobin level at the end of hospitalisation
- Change in the Activities of Daily Living (ADL) score pre-fracture and 6 months post-operatively.
A loss of independence will be defined as a decrease of one point or more in the ADL.

The reference value for haemoglobin levels was arbitrarily set at 5 days post-operatively. This is because haemoglobin levels recorded in A&E or on admission to the ward prior to surgery, or immediately post-operatively, may be influenced by factors other than isolated anaemia. Dehydration, present in the emergency department or on admission to the ward before the operation, corrected preoperatively, and postoperative haemodilution due to fluid replacement, cause the haemoglobin level to vary without there being any real deglobulation. We therefore postulate that the haemoglobin level on the 5th postoperative day can serve as a reference.

Confounding factors collected

All confounding factors related to loss of autonomy will be collected:

- Transfusion and number of red blood cell concentrates received

The indication for transfusion is at the discretion of the prescriber. However, it is generally accepted to transfuse patients with haemoglobin levels below 8 g/dL, or below 10 g/dL in cases of ischaemic heart disease or poor clinical tolerance.

- Age
- Gender
- Height, weight, Body Mass Index (BMI) calculation
- Screening for past or present higher brain function disorders
- Screening for major sensory disorders
- Screening for depressive symptoms: Mini Geriatric Depression Scale (MiniGDS)
- Comorbidities assessed using the Cumulative Illness Rating Scale - Geriatrics (CIRS-G)
- ASA score
- Number of medications (per class) taken by the patient (anticoagulants, antiplatelet agents, NSAIDs, anti-osteoporotic drugs, analgesics)

- Lifestyle and living environment
- Severe fractures before and after inclusion
- Other falls during the year
- Protein-energy malnutrition
- Iron deficiency (ferritin < 30 µg/L or CRP > 20 mg/L associated with a transferrin saturation coefficient < 15%)
- Recurrence of falls at 1, 3 and 6 months post-op

2.2. *SECONDARY OBJECTIVES AND EVALUATION CRITERIA*

2.2.1. *Secondary objectives*

The secondary objectives are to analyse:

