4. STUDY DESIGN AND PROCEDURE

4.1. STUDY SCHEDULE

The inclusion period will be 42 months. Follow-up is 6 months post-operative.

Patients may be included up to 48 hours after their arrival in the orthopaedic/orthopaedic surgery department.

a. D0 - Arrival in the orthopaedic/orthopaedic surgery department (after surgery)

Provision of the information leaflet and collection of non-objection after a reflection period.

Completion of the ASA score (*investigator*)

Biological tests (complete blood count (CBC), CRP, ferritin, transferrin saturation coefficient, albumin, vitamins B12, folate and vitamin D) (*investigator – performed on arrival at A&E or on admission to the department before surgery*)

Record of severe fractures prior to inclusion: upper end of the femur or humerus, proximal tibia, distal femur, 3 simultaneous ribs, wrist, pelvis and spine (Grio 2011 recommendations) (*investigator*)

Screening for previous or current upper function disorders (*investigator*)

Screening for major sensory disorders (*investigator*)

Completion of ADL and IADL questionnaires: **information relating to the week preceding the intervention** (*investigator: interview with patient, family or staff of residential care homes for elderly dependents (EHPAD)*)

Completion of the CIRS-G score (*investigator*)

Completion of the CAS questionnaire

Recording of lifestyle and living environment (*investigator*)

Number of medications (by class) taken by the patient on admission (anticoagulants, antiplatelet agents, NSAIDs, anti-osteoporotics, analgesics) (*investigator*) Completion of the MiniGDS score (*investigator*)

Collection of data on the procedure: time to surgery, type of fracture, surgical procedure, type of anaesthesia, weight-bearing authorisation, transfusion, number of red blood cell units received Haemoglobin measurement (if different from that taken in the emergency department or on admission to the ward before the procedure)

b. During the hospital stay: (trained orthopaedic nurses)

CAS score performed on days 1 to 3 post-operative, as well as on day 5 (or on discharge if this occurs before day 5)

Daily screening for confusion (CAM) until D10 if the patient is still hospitalised Completion of ADL questionnaires (*patient, family or nursing home resident interview*) on D5 post-operative (or on discharge if this occurs before D5)

Measurement of grip strength – Hand Grip on day 5 (or upon discharge if this occurs before day 5)

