5.2.1. Description of methods planned planned, including the schedule for planned interim analyses

All variables collected will be described by minimum, maximum, quartiles, mean and standard deviation for quantitative variables and by number and percentage of each modality for qualitative variables.

Analysis of the primary endpoint:

The relationship between loss of independence at 6 months and post-operative anaemia will be analysed using a logistic model. If a link is found, a multivariate analysis will be performed to confirm the independence of the anaemia/independence relationship. To do this, all potential confounding factors will be tested in a univariate analysis. Factors associated with a p value <0.20 will be retained in the multivariate model.

Analysis of secondary criteria:

- The analysis of the relationship between loss of autonomy on day 5 (or on discharge from hospital if discharged before day 5), at 1 and 3 months, and post-operative anaemia will be performed using the same method as for the primary endpoint.
- The 6-month mortality rate will be estimated with its 95% confidence interval using the Kaplan-Meier method.

The association between anaemia and mortality at 6 months will be studied using a Cox proportional hazards model in order to take confounding factors into account.

- The progression of post-operative anaemia (D0 to D15) will be described graphically.

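### Admission haemoglobin is measured but is not a listed confounder or a named model term, so the planned analysis does not separate anaemia carried in from anaemia acquired around surgery

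*Combined protocol and SAP*

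**What the plan says.** - **Exposure (2.1.2).** "Haemoglobin level on day 5 post-operatively (considered the post-operative haemoglobin reference level in this study". For patients transfused post-operatively, the end-of-hospitalisation value replaces it. Both are absolute levels, not changes from admission.
- **Pre-operative measurement (4.1, D0).** The schedule lists "Biological tests (complete blood count (CBC), CRP, ferritin, transferrin saturation coefficient, albumin, vitamins B12, folate and vitamin D", and says these are "performed on arrival at A&E or on admission to the department before surgery". A blood count includes haemoglobin.
- **Confounders (2.1.2).** "All confounding factors related to loss of autonomy will be collected", followed by 16 items. Admission haemoglobin and pre-operative anaemia are not among them. The nearest is "Iron deficiency (ferritin < 30 µg/L or CRP > 20 mg/L associated with a transferrin saturation coefficient < 15"%), which is one cause of anaemia and not its level.
- **Models (5.2.1).** If a crude link is found, "all potential confounding factors will be tested in a univariate analysis", and those with p<0.20 enter the multivariable model, whose purpose is to confirm that the relationship is independent. No covariate is named or forced in. The mortality Cox model refers only to confounding factors in general.
- **Background (1.1).** In a cited cohort of 546 patients, "40.4% had anaemia on admission and 93.0% had anaemia postoperatively". In a cited study of 395 patients, anaemia on admission "was correlated with a longer hospital stay and higher mortality at 6 and 12 months".
- **Dehydration (2.1.2).** The plan explains that admission values are distorted by dehydration and so are not used as the reference level. It does not discuss admission haemoglobin as a covariate.

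**The concern.** Apart from any transfusion, day-5 haemoglobin is the admission level minus the peri-operative loss. The admission level precedes the exposure, is a component of it, and may mark chronic disease that also affects recovery and survival. A low day-5 value can therefore mean a large loss around surgery, or a patient who arrived anaemic, and the named analyses treat the two alike.

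This matters because of how the result is to be used. Section 1.2.1 wants to derive a standardised protocol for managing post-operative anaemia, and section 5.2.1 offers the multivariable model as evidence of an independent relationship. Both uses need some view of the post-operative component. The secondary criterion in 2.2.2 does not supply it, because it includes the emergency-department and ward-admission values among the time points of the lowest post-operative haemoglobin and so mixes the two periods further.

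**Working it through.** **1. The plan's own figure.** Section 5.2.2 gives 255 analysable patients. 210 per year × 1.5 years = 315, and 315 × 0.9 × 0.9 = 255.15, so it reproduces. Adding a covariate does not change it.

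**2. Events available.** Section 5.2.2 cites 67.8% regaining their previous independence (a 12-month figure, applied here to 6 months). 255 × (1 − 0.678) = 82 events, or about 8 terms at the plan's 10 events per term. If all 16 listed items plus day-5 haemoglobin entered as one term each, there would be 82.1/17 = 4.8 events per term. With admission haemoglobin added, 82.1/18 = 4.6.

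**3. How much anaemia may be carried in.** 40.4/93.0 = 0.43. So about 43% of post-operatively anaemic patients were already anaemic on admission, if all those anaemic on admission stayed so.

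**4. Possible size of the bias.** The documents give neither the spread of admission haemoglobin, nor the spread of the fall, nor the effect of admission haemoglobin on ADL. All three are assumed: admission SD 1.4 to 1.6 g/dL, fall SD 1.0 to 1.6 g/dL, fall independent of admission level and without effect on the outcome, no transfusion, haemoglobin continuous. A model with day-5 haemoglobin alone then returns approximately

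OR(day 5) ≈ OR(admission)^w, with w = SD(adm)² / [SD(adm)² + SD(fall)²].

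For SDs 1.6 and 1.2: w = 2.56/(2.56 + 1.44) = 0.64, and 0.8^0.64 = 0.87. Simulation of 400,000 patients per scenario agrees to within 0.01 and gives, over the assumed SDs:

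| Assumed admission OR per g/dL | Day-5-only OR | With admission Hb, error-free |
|---|---|---|
| 0.70 | 0.78 to 0.86 | 1.00 |
| 0.80 | 0.85 to 0.91 | 1.00 |
| 0.95 | 0.96 to 0.98 | 1.00 |
| 1.00 | 1.00 | 1.00 |

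A second set of assumptions (correlation 0.3 to 0.7 between the two values; OR 1.25 to 2.0 per SD lower admission haemoglobin; n = 255) gives day-5-only ORs of 1.07 to 1.61 per SD lower. The day-5 coefficient is then significant in 9% to 93% of datasets, against 4% to 6% with adjustment. These are false positives only for a claim about the post-operative component, and this set does not include a null effect of admission haemoglobin.

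**5. Dehydration error.** Suppose recorded admission haemoglobin carries independent random error with SD s. The weight left on day-5 haemoglobin after adjustment is (1/SD(fall)²) / [1/SD(adm)² + 1/SD(fall)² + 1/s²]. With SDs 1.6 and 1.2 and s = 1.0: 0.694/(0.391 + 0.694 + 1) = 0.33, so the OR is 0.8^0.33 = 0.93, against 0.87 unadjusted. By simulation at s = 0.5, 1.0 and 1.5 g/dL, the adjusted OR is 0.97, 0.93 and 0.90. Adjustment removes about 78%, 46% and 29% of the bias.

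**6. Precision.** In the same scenario, scaled to n = 255, the standard error of the day-5 log odds ratio goes from about 0.07 to 0.11 per g/dL. This matches the variance inflation 1/(1 − 0.64) = 2.8, whose square root is 1.67: 0.069 × 1.67 = 0.115.

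**The case against.** **The cited evidence on function points the other way.** The study that links admission anaemia to mortality also found no difference in ADL, IADL or functional autonomy at 3, 6 and 12 months. A second cited cohort, of 550 patients, found no correlation of pre- or post-operative haemoglobin with motor function at day 60. This stands as a reason not to assume material bias on the primary endpoint. It is not decisive: the first cohort was previously autonomous, living at home and cognitively intact, restrictions that section 3 does not impose. The mortality finding still bears on the Cox model.

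**Listed covariates may absorb part of the effect.** CIRS-G, ASA, malnutrition and iron deficiency are all candidates, and the simulation above has none of them. If admission haemoglobin acts only as a marker of frailty (assumed correlation 0.5), adjusting for a frailty measure of reliability 0.5, 0.7 or 0.9 moves a spurious 0.86 to about 0.92, 0.95 or 0.985. If the proxy correlates only 0.4 with an admission haemoglobin that acts directly, the OR moves by just 0.01 to 0.02. The documents cannot decide between these.

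**Section 5.2.1 might already include it.** The screen covers all potential confounders without listing them, so admission haemoglobin could be admitted. But the only list omits it, and even if admitted it would have to pass the p<0.20 screen.

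**The primary objective (2.1.1) is a relationship with the severity of post-operative anaemia, whatever its origin.** This stands. It argues against making the adjusted version the sole primary model, which would change the quantity being estimated. It does not argue against reporting both.

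**Conclusion.** The point holds as a gap in the planned analysis. Admission haemoglobin is collected, is absent from the only confounder list and is named in no model, so the plan as written does not distinguish carried-in from acquired anaemia. The gap affects interpretation as an independent relationship, and the intended use for post-operative management, more than it affects description of an association.

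The size is unknown. The range of 0.78 to 1.00 per g/dL rests on assumed SDs and odds ratios, on a day-5-only model, and on no true effect of the fall. It includes no bias at all.

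A reader might infer three stronger things that the documents do not support:
- That the study cannot separate the two. It can, because the value is collected.
- That the ADL result will be materially biased. The cited functional results are null, and no odds ratio for ADL loss per g/dL of admission haemoglobin is given.
- That adjustment would isolate the effect of the post-operative fall. Dehydration error leaves part of the bias in place, and the end-of-stay substitution for transfused patients breaks the simple admission-minus-loss reading.

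**What to change.** - Add admission (pre-operative) haemoglobin to the confounder list in 2.1.2.
- In 5.2.1, pre-specify that the multivariable logistic models and the mortality Cox model are each reported with and without it, entered regardless of the p<0.20 screen.
- State the reading in advance. The model without it describes post-operative anaemia whatever its origin; the model with it approximates the post-operative component. Dehydration error in the admission value, and the end-of-stay value used for transfused patients, leave that separation incomplete.

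The cost is some SAP wording and one term, with no new data collection. The term draws on about 82 expected events that already fall short of 10 per candidate item, and the standard error for day-5 haemoglobin widens from about 0.07 to 0.11 per g/dL at n = 255 under the assumed SDs. Reporting both versions keeps the more precise estimate alongside the adjusted one.

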- **Record of transfusions** and number of red blood cell concentrates administered.

- Occurrence of **cardiovascular complications**: deep vein thrombosis, pulmonary embolism, myocardial ischaemia (increased troponin).

- Occurrence of a **neurological complication**: stroke, cerebrovascular accident, etc.

- **Post-operative bleeding** (including localised bleeding and gastrointestinal bleeding)

- Need for **repeat surgery**

- Occurrence of **haematomas**

- **Record of falls**

- **Vital status**

Post-operative M1, M3 and M6:

- Occurrence of **infection** (surgical site, pulmonary, urinary, skin, other), requiring antibiotic therapy.
- Occurrence of **acute urinary retention** requiring urinary catheterisation
- Occurrence of **dislocation/loosening of prosthesis**
- Occurrence of a **cardiovascular complication**: deep vein thrombosis, pulmonary embolism, myocardial ischaemia (increased troponin)
- Occurrence of a **neurological complication**: stroke, etc.
- Need for **repeat surgery**
-
- Record of recurrent **falls or fractures**
- Record of **new hospitalisations** and reasons
- **Vital status**

e. On geriatric assessment

- **CIRS-G(28) scale (in-hospital - inclusion):**

This is a comorbidity scale frequently used in studies because it provides a description of the health status of a population, describing chronic conditions and diseases that have an impact on autonomy, with good reliability and reproducibility

(29). For 14 major systems or groups of systems (cardiac, vascular, pulmonary pathologies, etc.), a score out of 4 is given: 1 being a mild pathology (chronic sinusitis or smoking less than 20 pack-years, for example), 4 is a severe condition causing disability or requiring immediate treatment (acute urinary retention or stroke with hemiparesis).

- **ASA score (30) (in-hospital - inclusion)**

Scale used in anaesthesiology Classifying patients into 6 categories: 1: healthy patient,

2 : with moderate impairment of a major function,

3 : patient with severe impairment of a major function that does not result in disability,

4 : patient with severe impairment of a major function, which is disabling and life-threatening,

5 : moribund patient,

6 : patient declared brain dead whose organs are being harvested for transplantation.

- Screening for depressive symptoms: **MiniGDS** score (*intra-hospital – inclusion*).

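### The plan says ischaemic heart disease or poor tolerance changes who is transfused, and so which haemoglobin is analysed, but neither has its own covariate: residual confounding is likely, plausibly but not certainly towards no effect

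*Combined protocol and SAP*

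**What the plan says.** Section 2.1.2 makes haemoglobin on day 5 the reference exposure. For patients transfused postoperatively, "the reference haemoglobin level will be the haemoglobin level at the end of hospitalisation". The same section says of transfusion that "The indication for transfusion is at the discretion of the prescriber", and then reports the general custom: to "transfuse patients with haemoglobin levels below 8 g/dL, or below 10 g/dL in cases of ischaemic heart disease or poor clinical tolerance".

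The confounder list in 2.1.2 has 16 entries. One is "Transfusion and number of red blood cell concentrates received"; others are the CIRS-G, the ASA score and medication counts by class, including antiplatelet agents. Ischaemic heart disease and poor clinical tolerance are not on it. The D0 data in 4.1 do not name a cardiac history, and the cardiovascular items in 4.3 are postoperative complications. The CIRS-G is described in 4.3 as follows: "For 14 major systems or groups of systems (cardiac, vascular, pulmonary pathologies, etc.), a score out of 4 is given". The plan does not say whether the total or the separate items would be modelled.

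Section 5.2.1 fits a logistic model of loss of independence on anaemia and goes on to a multivariable model only if the first one shows an association. Covariates are chosen by univariate screening: "Factors associated with a p value <0.20 will be retained in the multivariate model".

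**The concern.** By the plan's own account, heart disease or poor tolerance changes the chance of transfusion at a given haemoglobin, and postoperative transfusion changes which haemoglobin is analysed. Both indications are thus tied to the exposure by construction. If they also worsen functional recovery, which is plausible in this population, they confound the primary association. Having transfusion in the model does not remove this, because the indication still differs at the same haemoglobin and transfusion status.

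Two things are at stake. The haemoglobin odds ratio may be distorted. And if the distortion hides the crude association, 5.2.1 never reaches an adjusted analysis. The secondary analyses of independence at day 5, 1 month and 3 months use the same method and share the problem.

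**Working it through.** **1. The plan's own figures (5.2.2).** Analysable patients: 320 × (1 − 0.10 − 0.10) = 256; 320 × 0.9 × 0.9 = 259.2; 210 × 1.5 × 0.9 × 0.9 = 255.15. The stated 255 reproduces. Events: 255 × (1 − 0.678) = 82.1, hence about 82 / 10 = 8 model terms at ten events each. The 67.8% is a 12-month figure from a cited cohort, so 82 is an approximation for this 6-month endpoint.

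**2. What the custom implies if followed to the letter (haemoglobin before any transfusion).**

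| | Heart disease | No heart disease, tolerance good |
|---|---|---|
| Not transfused | 10 g/dL or above | 8 g/dL or above |
| Transfused | below 10 g/dL | below 8 g/dL |

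In both rows heart disease goes with higher haemoglobin. If heart disease worsens recovery, low haemoglobin then looks less harmful than it is. Two things pull the other way: lower haemoglobin in heart disease patients to begin with, and loose use of the custom.

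**3. Simulation (400,000 patients per scenario).** From the documents: the 8 and 10 g/dL custom, 65% with haemoglobin below 10 g/dL, and about 32% losing independence. Assumed: haemoglobin SD 1.3 g/dL; transfusion raises it by 1.5 g/dL; heart disease prevalence 20% or 35%; heart disease OR 1.5 or 2.5 for loss of independence; haemoglobin 0 to 1.5 g/dL lower in heart disease patients; the heart disease threshold applied in all or half of cases. Model: logit P(loss) = a + ln(0.80) × reference haemoglobin + ln(OR) × heart disease. The true OR is 0.80 per g/dL higher haemoglobin. Estimated ORs, as ranges over prevalence and heart disease OR:

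| Haemoglobin in heart disease | Threshold applied | Crude | With transfusion |
|---|---|---|---|
| Equal | all | 0.840–0.919 | 0.847–0.927 |
| Equal | half | 0.823–0.862 | 0.830–0.875 |
| 0.5 lower | all | 0.823–0.880 | 0.832–0.897 |
| 0.5 lower | half | 0.803–0.818 | 0.811–0.835 |
| 1.0 lower | all | 0.806–0.820 | 0.821–0.855 |
| 1.0 lower | half | 0.766–0.790 | 0.794–0.806 |
| 1.5 lower | all | 0.777–0.791 | 0.810–0.833 |
| 1.5 lower | half | 0.733–0.776 | 0.773–0.793 |

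- With heart disease added, every scenario gave 0.796 to 0.806.
- With heart disease unrelated to outcome (run with equal haemoglobin), there was no bias (0.797 to 0.800).
- An imperfect cardiac proxy (sensitivity 0.80, specificity 0.85) moved 0.927 only to 0.890, and 0.847 to 0.837.

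Share of the log OR lost in the transfusion-adjusted model: 1 − ln(0.927)/ln(0.80) = 1 − 0.0758/0.2231 = 66% at the extreme; 1 − ln(0.847)/ln(0.80) = 1 − 0.1661/0.2231 = 26% at the lower end of the first row. At the other extreme, 1 − ln(0.773)/ln(0.80) = 1 − 0.2575/0.2231 = −15%, an exaggeration.

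**4. The second trigger.** The recovery of 0.80 in step 3 holds because heart disease was the only extra trigger. In separate runs with a true OR of 1.20 per g/dL lower haemoglobin (1/1.20 = 0.83 per g/dL higher), 20–30% of patients had poor tolerance with OR 2.0–2.5 for loss of independence. Adding heart disease alone then gave only 1.11 to 1.14.

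**5. Size against precision.** SE of the log OR ≈ 1 / (SD × √(n p (1 − p))). Here √(255 × 0.322 × 0.678) = 7.46, so the SE is 1/(1.3 × 7.46) = 0.103, or 0.134 with SD 1.0. The largest shift towards 1 is ln(0.927/0.80) = 0.147, or 1.1 to 1.4 SE. The shift to 0.847 is ln(0.847/0.80) = 0.057, or 0.4 to 0.6 SE.

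**The case against.** A reader might infer something stronger: that the plan adjusts for transfusion but ignores heart disease, and that the haemoglobin association is therefore biased towards no effect. The documents do not support that.

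- Transfusion is not guaranteed a place in any model. It is one candidate, behind the crude association and the 0.20 screen.
- Heart disease is not wholly ignored. The CIRS-G has a cardiac item, and nothing says that only the total is used; ASA score and antiplatelet use are candidates too. They are partial proxies and none is forced in.
- The direction is not settled. The indication is left to the prescriber, and the table shows little or reversed bias when heart disease patients start lower and the threshold is applied loosely.
- Conditioning on transfusion is not the main source of the problem: in the first row of the table the crude model is biased about as much. This is largely ordinary unmeasured confounding.
- Complete absence of the variable cannot be claimed. Appendix 5 (data collection) is listed but was not available, so the eCRF may already hold a cardiac history.

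It is also fair that many of the shifts are under one standard error, that about eight terms must serve 16 listed candidates, and that a heart disease term does nothing for poor tolerance. All of this limits the point. It does not remove it: the plan names two determinants of transfusion and gives neither its own covariate.

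**Conclusion.** The point holds as residual confounding by indication, likely in kind and uncertain in size. Bias towards no effect is the more plausible direction if the custom is largely followed and heart disease worsens recovery, but it is not certain. Under the assumptions shown, a true OR of 0.80 per g/dL became 0.77 to 0.93 with transfusion in the model and heart disease left out. The size depends on heart disease prevalence, its effect on function, its own link to haemoglobin and prescriber adherence, none of which the documents give. Adding heart disease removes the bias only if it is the sole extra trigger; with poor tolerance also at work the correction is partial. A new covariate would also go unused whenever a masked crude result stops the adjusted analysis, so the term and the condition for running the model have to change together.

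**What to change.** - In 2.1.2, add to the confounder list: *ischaemic heart disease before the fracture (yes/no, from the medical file; CIRS-G cardiac item if the file is unavailable)*. If the eCRF already holds this, only the list needs changing.
- In 5.2.1, state that this term stays in the adjusted haemoglobin model whatever its univariate p value, and that the adjusted model is run and reported whether or not the crude model shows an association.
- State as a limitation that poor clinical tolerance remains an unmeasured indication for transfusion, so the adjustment is partial.

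The cost is one eCRF field, which can be filled from the file for patients already enrolled, a few sentences of text, and one degree of freedom out of roughly eight supported by about 82 events. That term competes with other candidates. No change to transfusion practice is proposed.
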